## Data sources

The Danish Civil Registration System (DCRS) contains information on the CPR number, vital and migrant status, cohabiting status, and municipality of residence. The Danish Knee Arthroplasty Register (DKR) is nation-wide register that contains information on all primary knee arthroplasty procedures and revisions performed in Denmark, e.g., baseline characteristics as age, sex, BMI, at the time of TKA operation. The registry started in 1997 and the reporting to the registry became mandatory since 2006. DKR is known for high degree of coverage and completeness. The Danish Microbiology Database (MiBa) is a national database containing data from all samples received by the Danish clinical microbiology departments from both hospitals and general practices with complete coverage since 2010.

The Danish National Patient Register (DNPR) is a valuable tool for epidemiological research, providing longitudinal registration of diagnoses, treatments, and examinations derived from every hospital contact in Denmark with complete nationwide coverage since 1978. The Danish National Prescription Registry has kept information on all prescriptions for drugs dispensed by community pharmacies in Denmark since 1994 according to Anatomical Therapeutic Chemical (ATC) classification system (ATC codes). Data from the Danish National Prescription Registry does not include hospital dispensaries.

The Danish Registers on Personal Income and Transfer Payments contains more than 160 variables including salaries, entrepreneurial income, taxes, public transfer payments, capital income, private pension contributions, and pay-outs. In addition, Statistics Denmark provide more detailed registers on specific income transfers, including sickness benefit, old age pension, disability pension, and cash and unemployment benefits. The Danish Population Education Register provides information on education status on Danish population, and it carries high degree of validity and coverage.

## Study population

In order to be eligible, we will include adult patients with primary or secondary osteoarthritis (due to meniscus or cruciate ligament lesion) who underwent primary TKA between January 1, 2011, and February 28, 2021, and for whom weight and height data are available. Patients will be identified from the DKR. Patients are followed for 2 years, until first revision, death or migration, whichever comes first.

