## Covariates

The cohort will be divided into two groups at baseline: obese, defined as  $\text{BMI} \geq 30 \text{ kg/m}^2$ , and non-obese, defined as  $\text{BMI} < 30 \text{ kg/m}^2$ . For descriptive purposes and adjusting, we will be using the following pre-TKA exposure covariates: age (years) at the time of TKA, sex (coded as female=1; male = 0), household income (at the year before KA, categorized into quartiles), highest completed education (at the year of KA, categorized into 3 categories: <11, 11 to 15, and >15 years). Comedication (at least one redeemed prescription 365 days earlier to index KA - 60 days for antibiotics): 1) Glucose-lowering due to the association between DM and surgical complications. 2) Antithrombotic medications and 3) NSAIDs because of the possible postoperative bleeding-related complications and 4) Antiresorptives due to the possible increased risk of revision. The last covariate to be included in matching and adjustment is Elixhauser Comorbidity Measure (ECM) (at the year of KA, categorized into 3: 0, 1-2 and  $\geq 3$ ), ECM is validated comorbidity scoring measure that has shown highest discriminative ability for the occurrence of all categories of postoperative adverse outcomes following orthopedic surgeries.

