## Statistical Methods

We will use descriptive statistics to summarize baseline characteristics of the two groups and will compare them using standardized differences. The 2-year (730 days) cumulative incidence of PJI will be reported for both groups. Hazard ratios with corresponding two-sided 95% confidence intervals (CIs) will be estimated using a Cox proportional hazards regression model. We will fit both unadjusted (crude) models and propensity adjusted models using inverse probability of treatment weighting (IPTW). For the adjusted model, propensity scores will be calculated based on age in years, female sex, completed education, household income, comedications, and ECM (all collected prior to surgery). Subsequent stratified analyses will categorize the observed PJI cases by bacterial infection type (within the first 90 days postoperatively or between 91 days and 2 years) and compare crude proportions between groups based on the absolute risk difference with 95% confidence intervals.

[figure not shown]
We present several analyses corresponding to the main results with 95% confidence intervals rather than P values, and comply with 2 Acta Orthopaedica principles for concluding whether scientifically important differences exist:

- A statistically non-significant test is not sufficient to claim "no difference." To show "no difference," a smallest clinically relevant size of the difference (it might be 0) must be defined. If all clinically relevant differences are excluded from the difference's confidence interval, a "no difference" or similarity/comparability conclusion is reasonable.
- A statistically significant test does not necessarily imply a clinically important difference. The importance of the tested null hypothesis depends on the smallest clinically relevant difference that should be defined a priori. If the difference's confidence interval excludes all clinically irrelevant differences, a conclusion concerning the existence of a clinically important difference is reasonable.

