To evaluate imprecision in the estimated treatment effect, a clinically important difference must first be defined. Based on an expected 2-year incidence of PJI of about 1%, a 50% increase in risk would be considered clinically relevant. In a time-to-event analysis, this corresponds to a hazard ratio of 1.5. Accordingly, non-inferiority—or absence of a clinically meaningful increase in risk—will be established if the upper bound of the 95% confidence interval for the hazard ratio remains below 1.5. We will visualize the 2-year cumulative incidence of all outcomes for both groups using the cumulative incidence functions (CIFs).

**Handling of missing data and sensitivity analyses:** Missing data is unavoidable in epidemiological and clinical research and must be explained otherwise it could undermine the credibility and validity of the research results. Missing values, for either predictors or outcomes, occur in all types of medical research. Unless prompted to do otherwise, most statistical packages explicitly exclude individuals with any missing value on any of the data analyzed. The resulting so-called "available case" or "complete case" analysis is the most common "default approach" to handle missing data, although it is rarely justified. Subjects with missing weight or height will be excluded from the analysis. Missingness of data on some of the covariates used for adjusting will be ignored but the subjects will not be excluded. Patients who will be lost during the follow up period (e.g., due to death or migration) are expected to be extremely few and no systematic difference is expected to be seen.

Therefore, this missingness of outcome data will be assumed "Missing completely at random" (MCAR), as there is no evidence to suggest systematic differences between the missing values and the observed values and will be ignored. For the purpose of sensitivity, we will potentially re-do the main analysis where missing outcome data is replaced twice, using best-case imputation ( $y=0$ ; no PJI) and worst-case imputation ( $y=1$ , PJI yes).

[figure not shown]
**Figure 1 (Mockup):** study flow chart

**Table 1 (Mockup).** Baseline characteristics at time of total knee arthroplasty

|  | Obese | Non-Obese | Std. Diff |
|--|-------|-----------|-----------|
| Age, years                                 |       |           |           |
| Female Sex, no. (%)                        |       |           |           |

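### Year of surgery is missing from the propensity score and Table 1 of a ten-year cohort, so calendar-time confounding of the hazard ratio, if present, would be neither adjusted for nor visible

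*Combined protocol and SAP*

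**What the plan says.** All references are to the combined protocol and SAP.

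- **Study population:** eligible patients are adults with osteoarthritis "who underwent primary TKA between January 1, 2011, and February 28, 2021". Each is followed for up to two years, so outcomes run to early 2023.
- **Statistical Methods:** for the adjusted model, "propensity scores will be calculated based on age in years, female sex, completed education, household income, comedications, and ECM". The Summary and Covariates sections list the same variables. The Cox models are a crude one and one using inverse probability of treatment weighting (IPTW). Neither has a term for calendar period or is stratified by it.
- **Statistical Methods, organism comparison:** the plan will "compare crude proportions between groups based on the absolute risk difference with 95% confidence intervals". Nothing is adjusted for in that comparison.
- **Table 1 (mock-up):** there is no row for year of surgery.
- **Missing-data paragraph and Sensitivity analyses section:** no analysis uses calendar period.
- **Statistical Methods, decision rule:** with an expected two-year PJI incidence of about 1%, a 50% increase is taken as clinically relevant. Absence of a meaningful increase is declared if the upper 95% limit of the hazard ratio is below 1.5.
- **Data sources:** reporting to the knee arthroplasty register has been mandatory since 2006, and the microbiology database is described as "with complete coverage since 2010". Both dates precede the first eligible surgery.

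**The concern.** Year of surgery confounds the obesity contrast if it is related both to being obese at TKA and to having a recorded PJI. Over ten years either could drift.

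The Definitions section leaves room for drift in the outcome. A register-coded infection revision is sufficient alone, so the outcome depends on how surgeons code the cause of revision. The tissue criterion needs at least three deep samples, so it depends on how many are taken.

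Weighting on age, sex, education, income, comedication and comorbidity does not balance year of surgery, except by accident through correlated variables. Income quartiles might carry some calendar information if they are cut across the whole period, but the Covariates section does not say how they are cut. Since Table 1 omits year, a reader could not see an imbalance.

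At stake is the primary hazard ratio, because the plan attaches a fixed rule to its upper confidence limit.

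**Working it through.** **1. The plan's own figure.** A rise in two-year risk from 1.0% to 1.5% corresponds to a hazard ratio of ln(1 − 0.015)/ln(1 − 0.010) = 1.504. This reproduces the stated 1.5. The plan gives no sample size, event count or power.

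**2. Accrual window.** 1 January 2011 to 28 February 2021 is 10.16 years.

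**3. Shift in the ratio when year is ignored.** The documents give no trends, so the inputs are assumptions: ten equal yearly cohorts, a linear change in the obese share p and in two-year PJI risk i, and no effect of obesity within any year. The apparent ratio is

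RR = [Σ(p·i)/Σp] / [Σ((1−p)·i)/Σ(1−p)].

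Example, with p from 35% to 45% and i from 0.8% to 1.2%:

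- obese: 0.04041/4.0 = 1.0102%
- non-obese: 0.05959/6.0 = 0.9932%
- RR = 1.0102/0.9932 = 1.017

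| Obese share | PJI risk | Apparent RR (true 1.00) |
|---|---|---|
| 35% to 45% | 0.8% to 1.2% | 1.017 |
| 35% to 45% | 0.7% to 1.4% | 1.029 |
| 35% to 50% | 0.7% to 1.4% | 1.042 |
| 38% to 44% | 1.2% to 0.7% | 0.987 |
| 35% to 45% | 1.2% to 0.7% | 0.978 |
| 35% to 50% | 1.2% to 0.7% | 0.968 |

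If either trend is flat, the ratio is exactly 1.00. At a 1% risk the risk ratio and hazard ratio are practically equal.

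**4. Steeper trends.** With the obese share going from 30% to 50% and PJI risk changing log-linearly by a factor of 0.5 to 3 (average 1%), a true hazard ratio of 1.00 appears as 0.953 to 1.078. A true 1.50 appears as 1.43 to 1.62.

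**5. Scale against sampling error.** Assume 20,000 to 60,000 TKAs, 1% events and 40% obese; the number of TKAs and the obese share are not in the documents. SE(log HR) = 1/√(events × 0.4 × 0.6), ignoring variance inflation from weighting.

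- 200 events: SE 0.144, 95% CI factor exp(1.96 × 0.144) = 1.33
- 600 events: SE 0.083, 95% CI factor 1.18

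The upward shifts in step 3 are ln(1.017)/0.144 = 0.1 to ln(1.042)/0.083 = 0.5 standard errors.

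**6. Effect on the 1.5 rule.** The chance that the upper limit falls below 1.5 is Φ{[ln 1.5 − ln(HR × bias)]/SE − 1.96}. With an assumed true hazard ratio of 1.2:

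| TKAs | No bias | Bias 1.04 | Bias 0.97 |
|---|---|---|---|
| 60,000 | 76% | 60% | 86% |
| 20,000 | 34% | 25% | 42% |

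**7. Organism rows.** With no true difference, an organism's share rising from 10% to 20% or 30%, and the obese share going from 30% to 50%, the spurious difference is 0.7 to 1.4 percentage points. Under the assumptions of step 5, with half the infections in each time window, the CI half-width for a 15% share is about 14 to 8 points.

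**The case against.** The strongest objection is that bias needs two trends at once, and the documents show neither. A reader might infer that secular change is in fact being attributed to obesity. The text does not support that: with either trend flat the bias is zero, and with opposing trends the ratio moves down. This stands, and the point can only be put conditionally.

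Second, the Data sources section suggests stable capture, because mandatory reporting and complete microbiology coverage both precede accrual, and one PJI definition covers the whole window. This stands for database coverage. It does not settle whether coding of the revision cause or the number of samples taken stayed constant.

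Third, the shift is small: at most about half a standard error in step 5. This also stands. Step 6 shows only that such a shift can alter the chance of meeting the rule when the true ratio makes the result a close call.

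Fourth, a reader might expect greater damage to the organism comparison. Step 7 does not bear this out. That comparison is deliberately unadjusted for everything, and its table footnote says the intervals should not be used in place of hypothesis testing.

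Finally, it would be too strong to say that leaving year out can only do harm. A variable related to obesity but not to the outcome causes no bias when omitted, and including it can cost some precision.

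**Conclusion.** The omission is confirmed: a cohort accrued over about ten years has year of surgery in no model and no table. Whether this biases the hazard ratio, and in which direction, cannot be told from the documents. Under the moderate trends assumed in step 3 the shift is about 1–4% either way; the steeper trends of step 4 reach 0.953 to 1.078. All these sizes rest on assumed trends.

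The practical consequence is confined mainly to a result whose upper limit lies near 1.5. The case for acting is that surgery date defines eligibility, so it is available for every included patient, precedes the outcome and is not plausibly a consequence of obesity. This is a cheap improvement of minor to moderate importance. It gives no reason to call the primary analysis invalid.

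**What to change.** - Add year of TKA, as calendar year or in two-year bands, to the propensity score.
- Add year of TKA with its standardized difference to Table 1.
- Optional check: stratify the Cox baseline hazard by the same bands.
- Optional description: show the organism rows for an earlier and a later period. This does not correct the crude organism comparison. With the assumed 200 to 600 infections split by obesity group, time window and two periods (eight columns), each column averages 25 to 75 infections over nine organism rows, so the table would be sparse and should be labelled descriptive.

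The cost is one covariate already in the register, one Table 1 row and possibly a slight loss of precision in the weights. The change should be written into the plan before the analysis is run.

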## Variables

### Outcomes and endpoints

1. The primary outcome is revision due to prosthetic joint infection (PJI) within 2 years following TKA
2. The first secondary outcome is types of microbial profiles detected in the PJs, short term ( $\leq 90$  days) and long-term (91 days to 2 years)
3. Another secondary outcome is revision due to all causes within 2 years following TKA.

For the revision due to PJI, we will stratify the outcome looking into the proportions of the following groups of bacteria within the first 90 days and between 91 and 730 days following TKA:

- A. PJI due to *Staphylococcus aureus*.
- B. PJI due to Coagulase-negative staphylococci.
- C. PJI due to other gram-positive bacteria.
- D. PJI due to gram-negative bacteria.
- E. PJI due to anaerobic bacteria.
- F. PJI due to mycoplasmic infection.
- G. PJI due to polymicrobial infection.
- H. PJI with negative culture.

## Definitions

**PJI:** our definition of PJI is adapted from The European Bone and Joint Infection Society (EBJIS) criteria as at least one of the following:

- A. DKR-registered revision surgery due to infection.
- B. At least 2 deep-tissue samples of phenotypically indistinguishable bacteria isolated from at least 3 deep-tissue samples
- C. One or more positive intraoperative samples from a closed fluid aspirate AND a biopsy (fluid AND tissue) of phenotypically indistinguishable bacteria isolated.

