## Sensitivity analyses

A sensitivity analysis will also be done to report PJI-likely revisions and the microbial profiles in these patients. PJI-likely revisions will be defined as revisions surgeries with at least one of the following: A) One single intraoperatively obtained positive culture obtained from the revision surgery (aspiration fluid OR tissue biopsy) regardless of the microorganism. B) One single positive culture obtained from aspiration of synovial fluid regardless of microorganism. If we do not find a difference between obese and non-obese, we will run a sensitivity analysis where we compare morbidly obese patients ( $BMI \geq 40 \text{ kg/m}^2$ ) with other patients ( $BMI < 40 \text{ kg/m}^2$ ). If the primary analysis showed a difference between obese and non-obese, a sensitivity analysis comparing morbidly obese ( $BMI \geq 40 \text{ kg/m}^2$ ) with non-morbidly obese ( $BMI 30-40 \text{ kg/m}^2$ ) will be done.

**Sensitivity analysis table 1:** Incidence for Periprosthetic joint infection-likely (PJI) revision at 2 years in obese and non-obese patients with the relative risk (RR) and an unadjusted and adjusted analyses of the Hazard Ratios (HR) between the 2 groups

|                           | Obese   | Non-Obese | HR [95% CI*]  |
|---------------------------|---------|-----------|---------------|
| Crude analyses:    |         |           |               |
| N                         | xx      | xx        |               |
| PJI-likely, no. (%)       | xx (xx) | xx (xx)   | xx [xx to xx] |
| Adjusted analyses: |         |           |               |
| N                         | xx      | xx        |               |
| PJI-likely, no. (%)       | xx (xx) | xx (xx)   | xx [xx to xx] |

\*CI: Confidence Interval

**Sensitivity analysis table 2:** Prosthetic joint infection-likely (PJI-likely) within the first 90 days and in 91 days-2 years postoperatively stratified by the type of infection

|   | Obese   | Non-Obese | Absolute Risk difference [95% CI*] |
|---|---------|-----------|------------------------------------|
| N   | xx      | xx        |                                    |
| PJI-likely, 90 days, no. (%)           | xx (xx) | xx (xx)   | xx [xx to xx]                      |
| Staphylococcus aureus, no. (%)                | xx (xx) | xx (xx)   | xx [xx to xx]                      |
| Coagulase-negative staphylococci, no. (%)     | xx (xx) | xx (xx)   | xx [xx to xx]                      |

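### PJI criteria B and C admit only bacteria and list A–H has no fungal group, yet Table 3 reports fungal PJI; a culture-confirmed fungal case counts only if the DKR codes the revision as infection

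*Combined protocol and SAP*

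**What the plan says.** Under Definitions, PJI is met "as at least one of the following":

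- Criterion A is "DKR-registered revision surgery due to infection". No culture or organism condition is attached.
- Criterion B is "At least 2 deep-tissue samples of phenotypically indistinguishable bacteria isolated from at least 3 deep-tissue samples". The organism must therefore be bacterial.
- Criterion C carries the same restriction in its own wording: "One or more positive intraoperative samples from a closed fluid aspirate AND a biopsy (fluid AND tissue) of phenotypically indistinguishable bacteria isolated".

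Outcomes and endpoints makes revision for PJI within 2 years the primary outcome. It then splits PJI into eight groups, A to H, introduced as groups of bacteria. Group F is "PJI due to mycoplasmic infection". No group is fungal.

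Table 3 (Mockup), which reports the microbial profile of the PJI revisions, has a fungal row for the first 90 days and another for 91 days to 2 years. Sensitivity analysis table 4, on PJI in morbidly obese patients, has fungal rows as well.

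Sensitivity analyses defines PJI-likely among revision operations. Its first item needs one "positive culture obtained from the revision surgery", whatever the organism.

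Data sources describes the culture source, the Danish Microbiology Database (MiBa), as a "national database containing data from all samples received by the Danish clinical microbiology departments". Under Study population, follow-up runs for 2 years or "until first revision, death or migration, whichever comes first".

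**The concern.** The study's stated purpose is to describe how obesity relates to the microbial profile of PJI. The case definition should therefore treat organism classes alike, and the planned categories should cover every case that the definition lets in. Neither holds for fungi. Bacterial infections have three routes into the outcome and fungal infections have one, so the fungal row of Table 3 would be undercounted relative to the bacterial rows. Fungal cases that do get in cannot be placed in the list that defines the secondary outcome.

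A related gap sits in the same lines. B names no operation, knee or date. C says only that its samples are intraoperative. Because MiBa is not limited to knee revisions, the rule linking a sample to a DKR revision should be written down. The PJI-likely definition does this in part; the primary definition does not.

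**Working it through.** The point concerns wording, so the check sets the definitions side by side.

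**Step 1: routes into the outcome.** Take a revision with at least 2 concordant positive samples out of at least 3 deep-tissue samples.

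| Organism | DKR codes infection | Criterion A | Criterion B | Counted as PJI |
|---|---|---|---|---|
| Bacterium | yes | met | met | yes |
| Bacterium | no | not met | met | yes |
| Fungus | yes | met | not met | yes |
| Fungus | no | not met | not met | **no** |

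Concordant fluid and tissue under C give the same pattern. The organism decides the result only where the DKR does not code infection.

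**Step 2: list against table.** List A–H has 8 groups. Table 3 has 9 organism rows per window: *S. aureus*, coagulase-negative staphylococci, other gram-positive, gram-negative, anaerobes, fungal, mycoplasma, polymicrobial and culture-negative. 9 − 8 = 1, and the extra row is the fungal one. Group F cannot stand in for it, because Table 3 has separate mycoplasma and fungal rows. A purely fungal case admitted through A fits none of the 8 groups: it is not bacterial, not polymicrobial and not culture-negative.

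**Step 3: primary against sensitivity definition.** The fungal case in the last line of step 1 meets PJI-likely if a single positive culture is read as at least one. It would then appear in Sensitivity analysis table 2 but not in Table 3, although its culture evidence is as strong as B asks of bacteria. If single is read as exactly one, the case appears in neither table.

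**Step 4: does the hazard ratio move?** The only figure nearby is the margin in Statistical Methods: about 1% incidence, a 50% increase, hazard ratio 1.5. It reproduces: ln(1 − 0.015) / ln(1 − 0.010) = 1.504. If a share m of true cases is missed equally in both groups, the ratio is ln(1 − 0.015(1 − m)) / ln(1 − 0.010(1 − m)). For m = 1%, 2% and 5% (assumed) it stays at 1.504. The documents give neither the fungal share of PJI nor the share of fungal revisions that the DKR does not code as infection. They also do not say whether either differs by BMI. A count of lost cases cannot be computed.

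**The case against.** The strongest reply is that criterion A has no organism condition and any one criterion suffices, so fungal PJI can count. That stands, and it rules out saying that confirmed fungal PJI is excluded altogether. What remains is the narrower gap in the last row of the first table, plus the mismatch between list and Table 3, which exists whatever the case count.

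A reader might also infer that B lets any culture series count, for example from a foot or the spine. The documents do not support this. The primary outcome is a revision for PJI, follow-up stops at the first revision, B requires concordant deep-tissue samples and C requires concordant intraoperative fluid and tissue. An analyst would naturally match samples to the revision and date the event by it. The linkage rule is missing detail rather than an error. PJI-likely is no full model either: it is looser on culture evidence and names neither the index knee nor the first revision.

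A reader might go further and infer that unrelated cultures inflate the hazard ratio and reverse the 1.5 rule. With assumed unrelated rates of 0.2% in obese and 0.1% in non-obese patients, a ratio of 1.20 becomes (1.2 + 0.2) / (1.0 + 0.1) = 1.27. With an assumed 500 events and 40% obese, the estimate must lie below 1.5 × exp(−1.96 / √(500 × 0.24)) = 1.254. The arithmetic is right, but every added input is an assumption:

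- With 600 events the limit is 1.5 × exp(−1.96 / 12) = 1.274, and 1.4 / 1.1 = 1.273 passes.
- With 0.1% in both groups, a true 1.0% against 1.5% gives 1.46 instead of 1.50, the opposite direction.
- Only patients with an aseptic revision could be misclassified. If those are 1–4% of patients (assumed), rates of 0.1–0.2% overall mean that 2.5% (0.1/4) to 20% (0.2/1) of them have an unrelated concordant series. Nothing in the documents supports that.

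**Conclusion.** The point holds in a limited form. Criteria B and C and list A–H leave out fungi, while Table 3 and the PJI-likely definition include them. Followed literally, the plan counts a culture-confirmed fungal PJI only when the DKR codes the revision as infection, and gives a purely fungal case no outcome group. This follows from the text alone and needs no assumed rate.

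The consequence falls on the microbial-profile outcome, where the fungal row would be undercounted. The number of cases is unknown and probably small. No effect on the hazard ratio, its direction or the 1.5 rule should be claimed. The missing link between samples and the index-knee revision is a clarification to make in the same edit.

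**What to change.** - In Definitions, replace bacteria with microorganisms in criteria B and C.
- In Outcomes and endpoints, add a fungal group to list A–H and widen its introductory wording beyond bacteria, so that the list and Table 3 have the same categories.
- In Definitions, state that samples counted under B and C are those taken at the first revision of the index knee, matched to the DKR revision date within a fixed tolerance, and that the revision date is the event date. This also settles which of the two time windows an event falls in.
- In Sensitivity analyses, say whether a single positive culture means at least one or exactly one.

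The cost is SAP wording and a date match between DKR and MiBa. Samples with no matching revision no longer count. The edit should be made before the data are analysed, so that case status is not settled afterwards.
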